3.2. Study Design and Starting Dose Rationale

Refer to [Section 3.2](#) of the main body of the protocol.

3.3. Dose-Limiting Toxicity Evaluation and Determination of RP2D

During Phase 1b, subjects will be entered in group at each dose level based on the mTPI-2 method ([Guo 2017](#)). After the last subject in each group (minimum of 3 DLT evaluable subjects) has completed the DLT observation period or developed a DLT, the SET will evaluate all available safety data and make the decision whether to escalate, stay at the current dose or de-escalate the

dose cohort with the second group of subjects treated, based on the guidelines outlined in and in the SET charter. Based on emerging clinical data, the SET might decide to include additional cohorts or terminate individual cohorts if deemed necessary. No intra-subject dose escalations will be allowed throughout this study.

3.3.1. Definition of Dose-Limiting Toxicity for Phase 1b (Dose Escalation)

Toxicities will be graded for severity according to the NCI-CTCAE, version 5.0. Only toxicities that occur during the DLT evaluation period will be used to define DLTs and for dose escalation decisions, but toxicities that occur during the entire treatment period will be recorded and considered in decisions regarding the RP2D.

The DLT evaluation period for Phase 1b is defined as 1 full cycle (4 weeks) of erdafitinib and cetrelimab from the start of the first erdafitinib dose. Therefore, in the Standard Dose Levels, the DLT period is defined as the first 4-week cycle, whereas in the Alternative Dose Levels, the DLT period is defined as the first 2 cycles (8 weeks).

If the subject receives more than 75% of any of the study drugs in the DLT evaluation period, the subject will be evaluable for DLT. If the subject received less than 75% of each assigned dose due to reasons other than toxicities (eg, disease progression, missed appointments, non-compliance, subject withdrawal), the subject may be replaced with a new subject. All available safety data from subjects will be taken into consideration by the SET. Dose-limiting toxicities are defined as any of the events listed in [Appendix 1 Table 3](#).

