In the FIH study 63723283LUC1001, treatment with cetrelimab showed overall similar toxicity profile when compared to already approved compounds targeting the PD-1/PD-L1 pathway. Treatment with erdafitinib in the Phase 1 (Study 42756493EDI1001) and a Phase 2 trial (Study 42756493BLC2001) was linked to hyperphosphatemia, diarrhea, dry mouth, asthenia, stomatitis, constipation, and decreased appetite as the most frequently reported AEs, most of which were Grade 1 or 2 in severity and treatment was well tolerated.

Based on currently available clinical data from erdafitinib and cetrelimab as monotherapies as well as preliminary data from this study in Section 1.5.2, the safety profiles for erdafitinib and cetrelimab are anticipated to remain manageable. Given the potentially complementary mechanisms of action of erdafitinib and cetrelimab (PD-1 inhibitor), it is hypothesized that this combination will provide increased efficacy relative to either agent alone in patients with urothelial cancer. As stated in Section 1.5.2 no DLTs were observed in any of the cohorts and the recommended Phase 2 dose (RP2D) was established as 8 mg erdafitinib orally once a day with up-titration to 9 mg based on C1D15 phosphate level + 240 mg cetrelimab IV Q2W.

After the RP2D was determined, the DRC met (ad hoc) at the request of the sponsor to review safety data as of 08 January 2020 with a particular focus on stomatitis at the RP2D. At that time stomatitis occurred in 70% of patients (7/10) at the RP2D which was higher than the frequency with erdafitinib monotherapy. The average time to onset was approximately 20 days which was sooner than that for erdafitinib monotherapy. The majority of patients experiencing mucositis at

the RP2D required dose interruption. The DRC concluded that additional data was required to further evaluate the benefit-risk profile of the RP2D.

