11.3. Analysis Populations

The analysis populations for the Phase 1b dose escalation part of the study are defined as the following:

- The Treated Population will consist of all subjects who receive at least 1 dose of study drug(s).
- DLT Evaluable Population: This set consists of all DLT evaluable subjects (defined in Section 3.3.1) among the treated population.

The analysis populations for the Phase 2 dose expansion part of the study are defined as the following:

- The Treated Population will consist of all subjects who receive at least 1 dose of study drug(s). The Treated Population will be used for all safety analyses and for efficacy analysis unless otherwise specified in the Statistical Analysis Plan.
- The PK/PD Population will consist of all subjects who received at least 1 dose of study drug(s) and have at least 1 during treatment sample collected to determine the concentration or PD biomarker response.

Subgroup analyses will be performed as appropriate, and details will be specified in the Statistical Analysis Plan.

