Erdafitinib + cetrelimab + carboplatin (DL2D or DL2D1)

Erdafitinib, cetrelimab and carboplatin start concurrently on C1D1. A maximum of 4 cycles of carboplatin will be administered. The DLT period is 2 cycles (6 weeks).

Refer to [Appendix 2 Table 4](#) for an overview of the Phase 1b: erdafitinib + cetrelimab + platinum chemotherapy dose levels.

Erdafitinib + cetrelimab + platinum (cisplatin or carboplatin) chemotherapy cohort:

The starting dose is 8 mg erdafitinib (no up-titration); 360 mg Q3W cetrelimab, and either 50 mg/m² Q3W for cisplatin (DL2C) or AUC 4mg/mL/min Q3W for carboplatin (DL2D).

If based on the rules below, dose escalation for cisplatin is DL2C to DL2C1.

If based on the rules below, dose escalation for carboplatin is DL2D to DL2D1.

The following rules for escalation apply for the Phase 1b erdafitinib + cetrelimab + platinum (cisplatin or carboplatin) chemotherapy cohort:

- At least 3 subjects may be dosed in each dose level that will be explored.
- A staggered enrollment strategy will be applied to the first 3 subjects in a dose level. A minimal interval of 24 hours between a subject's first dose will be required.
- At least 3 subjects per dose level are required to complete the DLT evaluation period or be discontinued for DLT before the SET can determine the dose and schedule for the next dose cohort.
- The SET will evaluate all available data including, but not limited to, PK, PD, safety, and preliminary anti-tumor activity, and will decide whether to escalate, stay at the current dose, or de-escalate the dose level based on the mTPI-2 guidelines outlined in [Attachment 1](#). These are briefly explained for the case with 3 subjects treated at a specific dose of platinum (cisplatin or carboplatin) chemotherapy:
 - If no subject at a specific dose level of platinum (cisplatin or carboplatin) chemotherapy experiences a DLT, dose escalation may proceed. as guided by mTPI-2. The SET will confirm the dose level chosen for the next dose cohort.
 - If 1 out of 3 subjects at a specific dose level of platinum (cisplatin or carboplatin) chemotherapy experiences DLT during the DLT evaluation period, then the SET may decide to enroll additional subjects before escalating the dose of platinum-based chemotherapy.
 - If 2 out of 3 subjects at a specific dose level of platinum (cisplatin or carboplatin) chemotherapy experience DLT during the DLT evaluation period. The SET will confirm the dose level chosen for the next dose level.

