3.3. Dose-Limiting Toxicity Evaluation and Determination of RP2D

During Phase 1b, subjects will initially be enrolled into the starting dose of cisplatin or carboplatin (DL2C and DL2D) based on the mTPI-2 method. (Guo 2017) After the last subject in each group (minimum of 3 DLT evaluable subjects) has completed the DLT observation period or developed a DLT, the SET will evaluate all available safety data and make the decision whether to escalate, stay at the current dose or de-escalate the dose of platinum chemotherapy with the second group of subjects treated, based on the guidelines outlined in and in the SET charter. Based on emerging clinical data, the SET might decide to adjust the dose of cisplatin and/or carboplatin or terminate individual dose levels if deemed necessary. No intra-subject dose escalations will be allowed throughout this study.

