3.3.1. Definition of Dose-Limiting Toxicity for Phase 1b (Dose Escalation)

Toxicities will be graded for severity according to the NCI-CTCAE, version 5.0. Only toxicities that occur during the DLT evaluation period will be used to define DLTs and for dose escalation decisions, but toxicities that occur during the entire treatment period will be recorded and considered in decisions regarding the RP2D.

The DLT evaluation period for the Phase 1b erdafitinib + cetrelimab + platinum (cisplatin or carboplatin) chemotherapy cohort is defined as 2 full cycles (6 weeks) of erdafitinib, cetrelimab, and platinum chemotherapy from the start of the first erdafitinib dose.

If the subject receives more than 75% of any of the study drugs in the DLT evaluation period, the subject will be evaluable for DLT. If the subject received less than 75% of each assigned dose due to reasons other than toxicities (eg, disease progression, missed appointments, non-compliance, subject withdrawal), the subject may be replaced with a new subject. All available safety data from subjects will be taken into consideration by the SET. Dose-limiting toxicities are defined as any of the events listed in [Appendix 2 Table 3](#).

Appendix 2 Table 3: Dose-Limiting Toxicity Criteria for Phase 1b: Erdafitinib + Cetrelimab + Platinum Chemotherapy cohort

Criteria for Non-hematological Toxicity	
	Exceptions
• Any Grade 3	Asthenia, anorexia, fever, or constipation
	Fatigue that improves to Grade ≤ 2 in ≤ 7 days
	Nausea lasting for ≤ 7 days responding to BSC ^a
	Vomiting and diarrhea that resolves in ≤ 3 days with BSC ^a
	Laboratory abnormalities that do not require hospitalization and are not felt to be clinically significant by the investigator
	Tumor flare (defined as local pain, irritation, or rash localized at sites of known or suspected tumor) that improves to Grade ≤ 2 in ≤ 7 days
	Elevation in AST or ALT for <7 days
• Any Grade 4	None
• Any Grade 5	None
• Elevation in AST or ALT >3 x ULN meeting criteria for Hy's law ^b	
Criteria for Hematological Toxicity	
Neutrophil count decreased: Grade 4 for >7 days	
Febrile neutropenia: Grade ≥ 3 or 4	
Platelet count decreased: Grade 3 with clinically significant bleeding or Grade 4	
Any Grade 5 toxicity	

Abbreviations: ALT=alanine aminotransferase; AST=aspartate aminotransferase; BSC=best supportive care; ULN=upper limit of normal.

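### DLT evaluability rests on exceeding 75% of any one study drug, so subjects under-exposed to the combination stay in the mTPI-2 denominator

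*Protocol*

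**What the plan says.** Section 3.3.1 of Appendix 1 (erdafitinib + cetrelimab) and of Appendix 2 (the same with platinum) carry one rule: "If the subject receives more than 75% of any of the study drugs in the DLT evaluation period, the subject will be evaluable for DLT". The next sentence says who may be replaced: "If the subject received less than 75% of each assigned dose due to reasons other than toxicities". Its examples include missed appointments and non-compliance. Section 10.2 of the main body adds only withdrawal before any dosing as a further ground, and otherwise refers back to 3.3.1.

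The same sections define the DLT window through the whole combination. In Appendix 1 it is "defined as 1 full cycle (4 weeks) of erdafitinib and cetrelimab from the start of the first erdafitinib dose", extended to two cycles (8 weeks) for the Alternative levels, where cetrelimab starts in Cycle 2. In Appendix 2 it "is defined as 2 full cycles (6 weeks) of erdafitinib, cetrelimab, and platinum chemotherapy from the start of the first erdafitinib dose".

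The evaluability rule feeds three other places:

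- Section 11.3, for the DLT Evaluable Population: "This set consists of all DLT evaluable subjects (defined in Section 3.3.1) among the treated population".
- Section 3.3 of both appendices, where the SET decides after a "minimum of 3 DLT evaluable subjects".
- Section 3.1.1 of Appendix 2 (with a matching rule in Appendix 1): "At least 3 subjects per dose level are required to complete the DLT evaluation period or be discontinued for DLT".

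Frequency and type of DLT is the Phase 1b primary endpoint. For the doublet, Section 1.8.1 reports that "no DLTs were observed in any of the cohorts".

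**The concern.** The question in Phase 1b is how toxic the combination is. A subject who took most of the daily tablets but missed half of the planned infusions, for a reason unrelated to toxicity, has not been tested on that combination. Under the rule as written this subject is a full member of the denominator, contributes a non-DLT if nothing happens, and cannot be replaced.

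If partial exposure is less toxic than full exposure, the observed DLT rate is biased downwards. That favours escalation, or staying where the table would otherwise de-escalate. Decisions can be taken on three subjects, so one such subject is a third of the evidence. Subjects who stop early because of a DLT are already counted correctly and are not at issue.

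**Working it through.** **1. How the two sentences fit together.** Take the fraction of planned dose received for each assigned drug. The first sentence makes a subject evaluable if the largest fraction exceeds 0.75. The second allows replacement if every fraction is below 0.75, so the largest is too. The two are complements only if *any* means *any one*; exactly 75% is covered by neither. A subject above 75% on one drug and below it on another is evaluable and not replaceable.

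**2. What this allows in doses.** Erdafitinib is daily. Infusion schedules are from Appendix 1 Table 4 and Appendix 2 Tables 1 and 4.

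| Levels | Window | More than 75% of erdafitinib days | Planned infusions in window | Still evaluable with |
|---|---|---|---|---|
| Standard | 28 days | 0.75 × 28 = 21, so ≥ 22 | cetrelimab 2 (Days 1, 15) | 22 days and 1 of 2 cetrelimab (50%) |
| Alternative | 56 days | 0.75 × 56 = 42, so ≥ 43 | cetrelimab 2 (Cycle 2, Days 1, 15) | 43 days and no cetrelimab |
| Platinum | 42 days | 0.75 × 42 = 31.5, so ≥ 32 | cetrelimab 2, platinum 2 (Day 1 of Cycles 1, 2) | 32 days and 1 of 2 cetrelimab and/or platinum |

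**3. The plan's own table.** Section 11.2 gives a target of 0.33 and an equivalence interval of 0.28 to 0.38. I assumed a Beta(1,1) prior, subintervals of length 0.10, and exclusion of a dose when the posterior probability of exceeding 0.33 is above 0.95; the protocol does not state the prior or the cut-off. On that basis all 49 cells of Attachment 1 are reproduced. The table is sound; the problem is who enters it.

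**4. Same DLT count, one extra under-exposed subject without a DLT.** From Attachment 1:

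- 1/3 is Stay; 1/4 is Escalate.
- 2/5 is De-escalate; 2/6 is Stay.
- 2/7 is Stay; 2/8 is Escalate.
- 3/7 is De-escalate; 3/8 is Stay.

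**5. Effect on decision probabilities.** Outcomes are taken as independent. Let p be the true DLT rate under full exposure and q the rate in an under-exposed subject. I assume p = 0.45 (above the 0.38 upper limit) and q from 0 to 0.20.

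*n = 3, one under-exposed:*

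- P(0/3), Escalate: all fully exposed 0.55³ = 0.166; with one under-exposed (1 − q) × 0.55² = 0.303 (q = 0) to 0.242 (q = 0.20).
- P(≥ 2/3), De-escalate: all fully exposed 3 × 0.45² × 0.55 + 0.45³ = 0.425; with one under-exposed 0.45² + q × 2 × 0.45 × 0.55 = 0.203 (q = 0) to 0.302 (q = 0.20).
- Mean DLT rate of the group: (2 × 0.45 + q)/3 = 0.300 to 0.367, inside the equivalence interval although p is above it.

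*n = 6, P(≤ 1 DLT), Escalate:*

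- All fully exposed: 0.55⁶ + 6 × 0.45 × 0.55⁵ = 0.164.
- One under-exposed: 0.256 (q = 0) to 0.215 (q = 0.20).
- Two under-exposed: 0.391 (q = 0) to 0.280 (q = 0.20).

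*Sensitivity to p, n = 3, one under-exposed:* P(0/3) goes from 0.216 to 0.288–0.360 at p = 0.40, and from 0.125 to 0.200–0.250 at p = 0.50. If q = p, nothing changes.

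**The case against.** **The completion rule protects the decision.** If the window means full cycles of every drug, three subjects who complete it have had every drug. But Appendix 1 restates the window as the first 4-week cycle or the first two cycles, and Appendix 2, Section 3.1.1 gives it as 2 cycles (6 weeks). Completing it is a matter of time and sets no dose per drug.

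**The wording may just be loose.** *Any of* could have been meant as *each of*. The replacement sentence points the other way, and if *each of* was intended the text still has to be corrected.

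**The figures presuppose an under-exposed subject.** This stands. With an assumed 5–10% chance per subject, p = 0.45 and q = 0–0.20, P(0/3) moves from 16.6% only to about 18–21% (0.5625³ = 0.178; 0.595³ = 0.211). A q of 0 is also extreme at the platinum levels, where such a subject has usually had one complete triplet Day 1.

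**The reach is narrow.** This largely stands. The doublet RP2D is set, and with no DLTs Attachment 1 says Escalate at every n from 3 to 9. Removing under-exposed subjects would change no cell unless fewer than three remained or a replacement had a DLT. DL1B enrolled nobody, and no escalation from DL2B is described. Each platinum agent has one escalation step, and the RP2D needs at least six subjects and all available data.

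**The SET sees everything and may add subjects.** This limits the harm, but does not remove these subjects from the count or from the Section 11.3 population.

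**Attachment 1 heads its columns by subjects treated, not DLT-evaluable.** Correct, and a further mismatch; these subjects are counted under either label.

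**Conclusion.** The concern holds. The evaluability rule in both appendices does not match the window it serves: it admits, and blocks replacement of, subjects who for non-toxicity reasons received half or less of a combination partner. They then enter the primary-endpoint denominator and the minimum group of three.

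The direction of bias is towards too low a DLT rate, provided partial exposure is less toxic. Its actual size cannot be stated, because the protocol gives neither the frequency of under-exposure nor the DLT risk under it. Section 5 of the working shows what one or two such subjects do in a small group; no wrong decision is claimed.

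The rule matters most for the platinum steps DL2C to DL2C1 and DL2D to DL2D1. The protocol describes these prospectively and does not say whether they are complete. For the doublet it bears only on how much weight the reported absence of DLTs can carry.

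**What to change.** Replace the two sentences in Section 3.3.1 of both appendices with a rule of this kind:

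*A subject is DLT-evaluable if he or she had a DLT in the DLT window; or completed the window and received at least 75% of the planned dose of each assigned study drug; or fell below 75% of any drug because of toxicity. A subject without a DLT who received less than 75% of any assigned drug for reasons other than toxicity is not evaluable and may be replaced.*

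This keeps the sponsor's 75% figure, settles the case of exactly 75%, and keeps poorly tolerating subjects in. Section 11.3 follows by its cross-reference. Attachment 1's column heading should be aligned so that the same subjects are counted throughout. For completed levels, report the doses of each drug received per subject in the window beside the DLT counts.

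The cost is a short edit in two appendices and possibly some replacements, which Section 10.2 already allows for non-evaluable subjects. With two planned infusions, 75% of each drug in practice requires both, so the rule is stricter than it looks. For the 2 × (3 + 6) = 18 planned platinum escalation subjects, an assumed 5–10% frequency gives 0.9 to 1.8, or about one or two replacements.

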Appendix 1 Table 3: Dose-Limiting Toxicity Criteria for Phase 1b: Erdafitinib + Cetrelimab Cohort

Criteria for Non-hematological Toxicity	
	Exceptions
• Any Grade 3	Asthenia, anorexia, fever, or constipation
	Fatigue that improves to Grade ≤ 2 in ≤ 7 days
	Nausea lasting for ≤ 7 days responding to BSC ^a
	Vomiting and diarrhea that resolves in ≤ 3 days with BSC ^a
	Laboratory abnormalities that do not require hospitalization and are not felt to be clinically significant by the investigator
	Tumor flare (defined as local pain, irritation, or rash localized at sites of known or suspected tumor) that improves to Grade ≤ 2 in ≤ 7 days
	Elevation in AST or ALT for < 7 days
• Any Grade 4	None
• Any Grade 5	None
• Elevation in AST or ALT $> 3x$ ULN meeting criteria for Hy's law ^b	

Criteria for Hematological Toxicity
Neutrophil count decreased: Grade 4 for >7 days
Febrile neutropenia: Grade ≥ 3 or 4
Platelet count decreased: Grade 3 with clinically significant bleeding or Grade 4
Any Grade 5 toxicity

Abbreviations: ALT=alanine aminotransferase; AST=aspartate aminotransferase; BSC=best supportive care; ULN=upper limit of normal.

- ^a Best supportive care (including electrolyte and hormone supplementation where clinically applicable) according to institutional standards or as outlined in Section 8.1.
- ^b Concurrent elevation of bilirubin >2 times institutional ULN without initial evidence of cholestasis and no alternative etiology for AST/ALT elevation.

3.3.2. Determination of the Phase 1b RP2D Regimen and Alternative Dosing Schedules

The RP2D of the erdafitinib + cetrelimab combination will be determined after review of all available PK, PD, safety, and efficacy data from at least 6 subjects treated at the RP2D and the recommended dose by mTPI-2 design. Only 1 RP2D will be tested in Phase 2.

The alternative dosing schedules, if explored, will be evaluated in a separate cohort distinct from dose escalation or dose expansion cohorts. The dose and schedule would be based on the totality of available data and decided by the SET or DRC.

The 4-week run-in of erdafitinib with subsequent concurrent dosing of erdafitinib and cetrelimab (eg alternative cohort DL2B) may be explored to further characterize the safety of the combination if the standard dosing schedule is identified as the RP2D. Subjects who meet appropriate molecular eligibility criteria at the time the RP2D is selected and who have had prior systemic treatment in the metastatic setting (ie, are not eligible for Phase 2) may be assigned 1:1 to the RP2D dose or the alternative cohort DL2B in consultation with the sponsor medical monitor if eligibility criteria are met. Subject safety will be monitored as indicated in Section 3.4. Cumulative safety evaluation will be performed after completion of Cycle 2 therapy for all subjects in each cohort (DL2B and RP2D).

3.4. Study Evaluation Team

Refer to Section 3.4 of the main body of the protocol.

4. SUBJECT POPULATION

Adult subjects age 18 years and older with metastatic or locally advanced urothelial cancer who meet the molecular eligibility and full-study eligibility are eligible for the study. Screening assessments will be performed as indicated in the Phase 1b erdafitinib + cetrelimab cohort Table and Events schedule ([Appendix 1 Table 1](#)). Molecular eligibility assessment may occur ≥ 28 days prior to administration of the study drugs.

The inclusion and exclusion criteria for enrolling subjects in this study are described in the following 2 subsections. If there is a question about the inclusion or exclusion criteria below, the

investigator should consult with the appropriate sponsor representative before enrolling a subject in the study. For a discussion of the statistical considerations of subject selection, refer to Section 11.1, Sample Size Determination.

